7.2 Trials Period

The following procedures/assessments will be performed on the days specified in the Schedule of Activities:

- Vital signs
- Weight
- ECOG performance status
- Physical exam
- Hematology, blood chemistry, coagulation, urinalysis, and per SoA
- Triplicate EKG (12 leads)
- Study drug compliance
- Adverse events
- Drug compliance
- Concomitant medications
- Tumor assessment: at the end of every even cycle (e.g., Cycles 2, 4, 6)
- Blood draws for PK/PD
- Urine collection

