8.2 Efficacy Evaluations

Assessment of response will be made using the International Myeloma Working Group response criteria (Palumbo et al, 2014). All patients' files and radiologic images must be available for source verification.

Imaging may include chest, abdomen and pelvis CT or MRI or PET/CT scans (when applicable); brain CT or MRI scan for patients with known CNS involvement; bone scan and/or bone x-rays for patients with lytic bone lesions, if applicable.

Tumor assessments conducted at baseline, at the end of every other cycle, whenever disease progression is suspected (e.g., symptomatic deterioration), and at the time of withdrawal from the study (if not done in the previous 6 weeks).

The same imaging technique used to characterize each identified and reported lesion at baseline will be employed in the following tumor assessments.

Assuming a background ORR of 10%, if the ORR on the current study for patients receiving ONC201 were 30% or higher there would be interest in further investigation of this treatment regimen. Therefore, this study will be used to detect a difference of 20% using a one- sided binomial test. Statistically, the hypothesis that will be tested is:

$H_0: p \leq 0.1$ versus $H_1: p > 0.3$

where p is the proportion of patients achieving an objective response. Enrollment of 30 patients will yield 84% power to detect a 20% difference at an alpha level of 0.05 (one-sided).

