10 DATA ANALYSIS/STATISTICAL METHODS

10.1 Efficacy Evaluation

All patients who have received a minimum of 2 cycles of study treatment had baseline assessments and at least one on-study tumor assessment following treatment will be considered evaluable for response.

Objective Response Rate (ORR) is defined as the proportion of patients with a Complete (CR) or Partial Response (PR) relative to the total number of evaluable patients. Responses will be defined according to the International Myeloma Working Group response criteria (see Appendix C: Multiple Myeloma Disease Tracking for Myeloma Worksheet).

The best overall response is the best response recorded from the start of treatment until disease progression/recurrence (taking as reference for progressive disease the smallest measurements recorded since the treatment started) or the withdrawal from the study. Stable disease will be considered the best response when observed at least after two months from baseline.

Tumor responses will be analyzed in a descriptive manner. The number and percentage of objective response (CR+PR) will be tabulated by dose level. An ORR may be summarized for the RP2D expansion cohort with the corresponding 95% exact confidence interval.

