10.2 Futility Analysis

A Bayesian method by Thall et al (1995) will be used for futility monitoring in Phase 2 of the study. The trial will be stopped early if $\Pr(\text{ORR} < 0.1 | \text{data}) > 0.95$. That is, the trial will be stopped early if there is more than a 95% probability that the ORR is lower than 10%. We assume that ORR follows a prior distribution of beta (0.1, 0.9).

The futility rules will be implemented once the first 12 patients have been enrolled in Phase 2. The corresponding stopping boundaries are listed in the following table 10.1. For example, if there are no responses in the first 12 patients enrolled in Phase 2, the trial will be terminated early due to futility. Multc Lean software V2.1 was used for the design. If the trial continues until 20 additional patients are evaluated, and 3 responses are observed among the 26 patients, then the 95% credible interval for the response rate would be (2.6%, 25.7%).

Table 10.1: Stopping boundaries for futility monitoring

# Patients (inclusive)	Stop the trial if there are this many responses total:

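### The futility look in Section 10.2 is timed by enrolment rather than by response assessment, and row 24-25 of Table 10.1 does not follow from the stated 0.95 cut-off

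*Combined protocol and SAP*

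**What the plan says.** Section 10.2 sets a Bayesian futility rule for Phase 2. The trial stops if "there is more than a 95% probability that the ORR is lower than 10" per cent, with a Beta(0.1, 0.9) prior. The start of monitoring is tied to enrolment: "The futility rules will be implemented once the first 12 patients have been enrolled in Phase 2". The worked example repeats this: "if there are no responses in the first 12 patients enrolled in Phase 2, the trial will be terminated early due to futility". Table 10.1 labels its rows only by number of patients. It stops at 0 responses for 12-23 patients and at 0-1 for 24-25, and gives 26 as the maximum. A later sentence in Section 10.2 speaks of patients being evaluated rather than enrolled.

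Other sections fix when a response can be known:

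- Section 7.2 lists "Tumor assessment: at the end of every even cycle (e.g., Cycles 2, 4, 6"). Section 8.2 also places assessments at the end of every other cycle, and Section 3.3 sets a cycle at 21 days.
- Section 10.1 opens its definition of evaluability with "All patients who have received a minimum of 2 cycles of study treatment", adds at least one on-study tumor assessment, and uses evaluable patients as the ORR denominator.

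Section 10.2 does not say whether the look waits for the 12 to be assessed, whether accrual pauses, or how patients awaiting assessment are counted.

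**The concern.** The 12th patient enrolled, and anyone enrolled in the preceding six weeks, has not reached a first tumor assessment when the 12th enrolment occurs. If the rule is applied at that moment, those patients add to the count of patients but cannot add to the count of responses. The same happens at every later row of Table 10.1. Because the rule ends Phase 2, any excess in the stopping chance falls on a regimen that meets the plan's own target of 30% ORR.

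The mismatch in row 24-25 is a separate matter. At 1 response in 24 or 25 patients the table stops the trial and the probability statement continues it. Whoever applies the rule there has two opposite instructions.

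**Working it through.** **Inputs.** Prior Beta(0.1, 0.9), reference ORR 10% and cut-off 0.95 (Section 10.2). Target ORR 30% and 30 patients (Section 8.2). First assessment at 2 × 21 = 42 days (Sections 3.3, 7.2, 8.2). Accrual of 30 Phase 2 patients in 24 months, or 1.25 a month (Section 3.2), or 42 patients in 24 months, or 1.75 a month (Synopsis). I assume that treatment starts at enrolment.

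**The plan's own figures.**
- With r responses in n patients the posterior is Beta(0.1 + r, 0.9 + n − r). At 0/12, Pr(ORR < 0.1) = 0.985, above 0.95, so the 0/12 boundary reproduces.
- At 3/26, Beta(3.1, 23.9) gives a 95% interval of 2.6% to 25.7%, as stated.
- Declaring success at 7 or more of 30 has one-sided alpha 2.6% at ORR 10% and power 84.0% at ORR 30%. This reproduces the 84% in Section 8.2, which therefore describes a fixed 30-patient test without futility stopping.

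**False stop with every patient assessed, ORR 30%.** At the first look it is 0.7^12 = 1.4%. Row 24-25 adds 0.1 points, so Table 10.1 as a whole gives about 1.5%.

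**False stop at the 12th enrolment, ORR 30%.** If k of the 12 are unassessed, the chance is 0.7^(12 − k).

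*Evenly spaced entry.* The gap between patients is 24 × 30.4375 / 30 = 24.4 days, or 24 × 30.4375 / 42 = 17.4 days.
- At 24.4 days, the 12th and 11th patients are inside 42 days: k = 2, 0.7^10 = 2.8%, ratio 2.0.
- At 17.4 days, the 12th, 11th and 10th are inside: k = 3, 0.7^9 = 4.0%, ratio 2.9.

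*Random (Poisson) entry.* Here k = 1 + a Poisson count with mean m = 42/24.4 = 1.72 or 42/17.4 = 2.41. Ignoring the cap at 12, the average of 0.7^(12 − k) is 0.7^11 × exp(m × (1/0.7 − 1)).
- m = 1.72: 0.0198 × exp(0.739) = 4.1%, ratio 3.0.
- m = 2.41: 0.0198 × exp(1.035) = 5.6%, ratio about 4.

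**Whole boundary and power.** Simulation of 200,000 trials per scenario, random entry, 42-day lag, ORR 30%. The 24-25 row is carried to 29 patients and success is 7 or more of 30, because Section 8.2 is written for 30.

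| Scenario | False stop | Power |
|---|---|---|
| All counted patients assessed | 1.5% | 83.5% to 83.7% |
| 1.25 a month | 4.4% | 82.0% |
| 1.75 a month | 5.9% | about 81% |
| 3 a month (assumption, faster than planned) | about 12% | 76.5% |

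With evenly spaced entry at the two planned rates, the whole boundary gives about 3% and 4.3%.

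**Shorter lag.** If response could be read at Cycle 2 Day 1 (21 days), the false stop at planned accrual is about 2% to 3.5%.

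**Row 24-25.** Pr(ORR < 0.1) is 0.905 at 1/24 and 0.914 at 1/25. It is 0.948 at 1/30 and first passes 0.95 at 1/31, beyond both the 26 in Table 10.1 and the planned 30. At 1/23 it is 0.894, so the row is what a 0.90 cut-off would give.

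**The case against.** **The wording may only name a cohort.** The first 12 enrolled can be read as the group to be monitored, with the look taken once they are assessed. The rule monitors ORR, Section 10.1 defines ORR on evaluable patients, Section 3.2 plans 30 evaluable patients, and Section 10.2 itself later speaks of patients evaluated. A reader might infer that the plan instructs pending patients to be scored as failures. It does not; that follows only from the literal reading. What stands is an ambiguity in a rule that ends Phase 2. Leaving pending patients out of the denominator does not by itself settle it if the look is still taken at the 12th enrolment. The posterior at 0/9 is 0.976 and at 0/10 is 0.980, both above 0.95, whereas Table 10.1 never stops with fewer than 12 patients.

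**The lag may be shorter than 42 days.** Table 1 schedules serum protein electrophoresis at Cycle 2 Day 1, and Section 7 gives that schedule precedence over its own text. This is fair, and is why the 21-day figures are given. Against it, Section 8.2 repeats the every-other-cycle assessment and Section 10.1 requires two cycles before a patient is evaluable.

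**The effect is modest.** This also stands. At planned accrual, power stays above 80%. A reader might infer an eightfold rise in false stops. That needs about 3 patients a month with random entry, which would fill Phase 2 in 10 months instead of the planned 2 years. The documents give no such rate.

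**The row 24-25 mismatch is unrelated to timing.** Agreed. At 30% ORR it changes the false stop only from 1.4% to 1.5%. It is reported as a second defect in the same rule.

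**Conclusion.** The point holds in two parts.

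First, the trigger in Section 10.2 conflicts with the evaluable denominator in Section 10.1 and the assessment schedule. Applied literally at planned accrual, it raises the chance of stopping a regimen with 30% ORR from about 1.5% to about 3% to 6%, and costs about 1.5 to 2.5 points of power under random entry (less with even spacing). This rests on three assumptions: a 42-day lag, treatment starting at enrolment, and the look being taken as each patient enrols. The documents state no false-stop rate for this rule, so the comparison is with what Table 10.1 implies on assessed patients, not with a declared target. Ratios above about 4 require accrual faster than planned or a longer lag.

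Second, row 24-25 of Table 10.1 contradicts the stated 0.95 cut-off. This is exact and depends on no accrual assumption. A reader might infer that 0.90 was the intended cut-off; the row fits it, but no section says so.

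**What to change.** 1. In Section 10.2 and Table 10.1, define the count as treated Phase 2 patients who have completed the end-of-Cycle-2 response assessment or left treatment before it. Count those who left early as non-responders.
2. Align the ORR denominator in Section 10.1 with that set. As it stands, Section 10.1 excludes patients with fewer than two cycles, so changing Section 10.2 alone would leave the interim and final analyses on different patients.
3. State whether accrual continues while assessments are pending.
4. Recompute Table 10.1 with one cut-off used in both text and table. Under 0.95, row 24-25 becomes 0. The choice matters most for an inactive regimen: at a true ORR of 10%, the chance of stopping on assessed patients is 38.9% with the present row and 28.2% without it.
5. Extend the table to the planned Phase 2 maximum, reconciling 26 in Table 10.1 with 30 in Sections 3.2 and 8.2. Correct the worked sentence on 20 additional patients too: counted from the first 12 they make 32, not 26.

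The cost is protocol wording, one recomputed table, and either a short accrual pause or about 2 to 4 more patients enrolled while the first 12 reach assessment.

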	# responders (inclusive)
1-11	Never stop with this many patients
12-23	0
24-25	0-1
26	Reach maximum number of patients, always stop

10.3 Early Stopping Rules for Safety/adverse events:

Adverse events will be assessed continuously throughout the study. During evaluation of the first cohort of 12 eligible patients, if 4 patients have to discontinue the study drug due to treatment-related adverse events, the study will be interrupted for consideration of dose reduction or termination. If 6 of a total of 26 eligible patients have to discontinue the study drug due to treatment-related adverse events the study will be suspended and early termination for excess toxicity will be considered after careful investigation of the causes of the higher than expected toxicities. Once the cause of the higher than anticipated toxicities has been determined, the study team will confer with the FCCC DSMC and IRB to make a determination whether accrual can be resumed or the study will be terminated early. The chance of early termination with a true toxicity of 30% is 51%. The chance of early termination in error (when true toxicity is 5%) is 0.2%. The overall study power is 85% (for detection of overly toxic treatment) and has type I error of 0.3%.

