3.2 Number of Patients

Phase 1 is expected to enroll up to 12 patients and Phase 2 will enroll up to 30 evaluable patients over the course of 2 years. The actual sample size will depend on the clinical results.

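### Table 10.1 ends Phase 2 at 26 patients while Sections 3.2 and 8.2 plan and power it on 30, so the end of accrual and the responder cutoff for success are not fixed

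*Combined protocol and SAP*

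**What the plan says.** **Size 30.** Section 3.2: "Phase 2 will enroll up to 30 evaluable patients over the course of 2 years", followed by "The actual sample size will depend on the clinical results". Section 8.2 sets a background ORR of 10% against 30%, tested by a one-sided binomial test: "Enrollment of 30 patients will yield 84% power to detect a 20% difference at an alpha level of 0.05 (one-sided"). The synopsis and Section 1 give 42 patients in all, which is the 12 of Phase 1 plus 30.

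**Size 26.** Section 10.2 applies Bayesian futility monitoring to Phase 2 and starts it there: "The futility rules will be implemented once the first 12 patients have been enrolled in Phase 2". The rule stops the trial when the posterior probability that the ORR is below 0.1 exceeds 0.95, and "We assume that ORR follows a prior distribution of beta (0.1, 0.9"). Table 10.1 never stops at 1-11 patients, stops with 0 responses at 12-23 and with 0-1 at 24-25, and at 26 says "Reach maximum number of patients, always stop". The worked example also uses 26: "If the trial continues until 20 additional patients are evaluated, and 3 responses are observed among the 26 patients", with a 95% credible interval of 2.6% to 25.7%. Section 10.3 bases its safety rule on 4 of the first 12 and 6 of a total of 26 eligible patients.

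**Success criterion.** No section states a number of responders. Section 10.1 says "Tumor responses will be analyzed in a descriptive manner"; the hypothesis test appears only in Section 8.2.

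**The concern.** Followed literally, Table 10.1 closes Phase 2 four patients short of the size on which the power is stated, whatever the results. A site that has treated its 26th Phase 2 patient has two instructions: stop, or continue to 30.

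The cutoff that satisfies alpha 0.05 depends on the size, so leaving the size open leaves the success criterion open too. In an open-label single-arm trial, both could then be settled after responses are known. A second question is whether the table's rows follow from the rule as stated. If they do not, adding rows up to 30 would carry an error forward.

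**Working it through.** **Inputs.** p0 = 0.10, p1 = 0.30, one-sided alpha 0.05, N = 30 (Section 8.2); N = 26, prior beta(0.1, 0.9), threshold 0.95, monitoring from 12 patients (Section 10.2); safety counts 4 of 12 and 6 of 26, with true toxicity 30% or 5% (Section 10.3).

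**1. The plan's power figure.** Exact binomial: alpha = P(X ≥ k | N, 0.10) and power = P(X ≥ k | N, 0.30), where k is the smallest count with alpha ≤ 0.05. At N = 30, k = 7, alpha = 0.0258 and power = 0.8405. This reproduces the stated 84%, so that figure belongs to 30 patients and an unwritten cutoff of 7.

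**2. Both sizes, with matched and mismatched cutoffs.**

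| N | Cutoff | Alpha | Power |
|---|---|---|---|
| 30 | ≥ 7 | 0.0258 | 0.8405 |
| 26 | ≥ 6 | 0.0399 | 0.8374 |
| 26 | ≥ 7 | 0.0119 | 0.7035 |
| 30 | ≥ 6 | 0.0732 | 0.9234 |

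**3. The plan's credible interval.** After x responses in n patients the posterior is beta(0.1 + x, 0.9 + n − x). For 3 of 26, beta(3.1, 23.9) gives 2.6% to 25.7%, as stated. For 3 of 30 it would be 2.3% to 22.5%. The example was therefore computed on 26. Its wording is unclear: monitoring starts at 12, and 12 + 20 = 32, not 26.

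**4. The plan's safety figures.** P(stop) = P(X ≥ 4 of 12) + Σ over x = 0 to 3 of P(X = x of 12) × P(Y ≥ 6 − x among the remaining patients).

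| True toxicity | First 12 | Total 26 | Total 30, same count of 6 |
|---|---|---|---|
| 30% | 0.5075 | 0.8495 | 0.9269 |
| 5% | 0.0022 | 0.0033 | 0.0049 |

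The stated 51% and 0.2% are the 12-patient look and do not depend on the total. The stated overall 85% and 0.3% match a total of 26.

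**5. Does Table 10.1 follow from its rule?** Pr(ORR < 0.1 | data) under the stated prior:

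| Responses / patients | Probability | Exceeds 0.95? |
|---|---|---|
| 0/12 | 0.9851 | yes |
| 1/23 | 0.8944 | no |
| 1/24 | 0.9047 | no |
| 1/25 | 0.9139 | no |
| 1/30 | 0.9485 | no |
| 1/31 | 0.9535 | yes |

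One response first triggers a stop at 31 patients. The stated rule therefore gives a boundary of 0 throughout 12-25 (or 12-29), not 0-1 at 24-25. A threshold of 0.90 would reproduce the printed rows (0.8944 at 23, 0.9047 at 24), but the documents do not state one.

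**6. Effect of the futility rule**, assuming a look after every patient from 12. Under the stated rule the only possible stop is 0 responses in the first 12: 0.9^12 = 0.2824 at a true ORR of 10% and 0.7^12 = 0.0138 at 30%. With the printed rows these become 0.3888 and 0.0148. Power with futility is 0.8344 for ≥ 6 of 26 (printed rows) and 0.8366 for ≥ 7 of 30 (regenerated rows).

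**The case against.** **The 30 is only a ceiling.** Section 3.2 foresees a smaller trial depending on results. That is true, but Table 10.1 stops at 26 whatever the results and calls that number the maximum.

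**26 may count something else.** It cannot be the evaluable part of 30, because Section 3.2 already says 30 evaluable. Six Phase 1 patients plus 20 more would make 26, but Section 10.2 counts patients enrolled in Phase 2.

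**The cutoff can be derived.** Section 8.2 gives the null rate, the test, alpha and N = 30, which imply at least 7; at 26 the same test implies at least 6. This stands in part. Only N is truly unresolved, and the mismatched figures (70.3% power, alpha 0.073) arise only if a cutoff is carried from one size to the other. They show why the cutoff should be written down; they are not results of the plan as printed.

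**The loss of power is negligible.** It is, with matched cutoffs: 84.05% against 83.7%.

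**The row for 24-25 patients is a separate error.** It is wrong at either size, and a software setting that the protocol does not describe might explain it. It belongs here because any repair of the maximum requires the table to be regenerated.

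**Section 10.3 could be a look at 26 within a larger study.** That is possible. The 30-patient safety figures describe a rule the protocol does not state, so this point is secondary. It remains fair to ask which patients are counted.

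**Conclusion.** The concern holds. The protocol rests on two Phase 2 sizes: enrolment and power use 30, while the futility table, its worked example and the overall safety characteristics use 26. Nothing in the text reconciles them. The consequence is a four-patient ambiguity in the end of accrual and a success cutoff of 6 or 7 responders depending on which size is followed; it is not a material loss of power. In addition, stopping with one response at 24-25 patients contradicts the stated 0.95 rule, and early stopping at a true ORR of 10% is 38.9% with the printed rows against 28.2% with the stated rule.

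The cutoffs assume an exact binomial test, which reproduces the stated 84%. The early-stopping figures assume a look after every patient from the twelfth. This must be corrected, because the maximum size and the success criterion for the primary endpoint have to be unambiguous before the data are read.

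**What to change.** State one Phase 2 maximum in every place, and say whether it counts enrolled or evaluable patients.

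- **If 30:** regenerate Table 10.1 from the stated prior and threshold (1-11 never stop; 12-29 stop at 0 responses; 30 maximum reached), and state success as at least 7 of 30 (alpha 0.0258, power 84.05%).
- **If 26:** restate Section 8.2 as at least 6 of 26 (alpha 0.040, power 83.7%), change 30 to 26 and 42 to 12 + 26 = 38, and correct the 24-25 row so that 12-25 stop at 0 responses.
- **In either case:** correct the worked example. If the boundary of 0-1 at 24-25 was intended, state the threshold that produces it instead of 0.95. Say in Section 10.1 that the Section 8.2 test and its cutoff apply. Say which patients Section 10.3 counts, reconcile it with the chosen maximum and restate its operating characteristics. The safety boundary itself is for the sponsor and the safety committee.

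**Cost:** wording in the synopsis and Sections 1, 3.2, 8.2, 10.1, 10.2 and 10.3, and one regenerated table. No patients beyond those already stated are needed. Applying the 0.95 rule as written does lower the chance of early stopping at a true ORR of 10% from 38.9% to 28.2%, and the sponsor should accept that knowingly.

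### The toxicity limit in section 10.3 and its 85% and 0.3% are set for 26 eligible patients, but sections 3.2 and 8.2 plan 30 in Phase 2

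*Combined protocol and SAP*

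**What the plan says.** Section 10.3 opens with "Adverse events will be assessed continuously throughout the study" and then gives two numerical rules. Four treatment-related discontinuations among the first 12 eligible patients interrupt the study. The second rule is: "If 6 of a total of 26 eligible patients have to discontinue the study drug due to treatment-related adverse events the study will be suspended". Early termination is then considered, and the study team confers with the centre's DSMC and the IRB "to make a determination whether accrual can be resumed or the study will be terminated early".

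Four operating characteristics follow. Two concern early termination: "The chance of early termination with a true toxicity of 30% is 51" per cent, and "The chance of early termination in error (when true toxicity is 5%) is 0.2" per cent. The other two are an overall power of 85% and an overall type I error of 0.3%.

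The maximum of 26 also appears in section 10.2, which is explicitly about Phase 2. The last row of Table 10.1, for 26 patients, reads "Reach maximum number of patients, always stop".

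Elsewhere the number is 30. Section 3.2 says "Phase 2 will enroll up to 30 evaluable patients over the course of 2 years". Section 8.2 computes 84% power for an enrolment of 30. The synopsis and section 1 give a study total of 42, which is the 12 of Phase 1 plus 30. Section 10.1 counts a patient as evaluable only after at least 2 cycles, a baseline assessment and one on-study tumour assessment.

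**The concern.** The two maxima cannot both hold. Evaluable patients are a subset of those enrolled, so 30 evaluable patients cannot come out of 26 eligible ones. A patient who stops for toxicity before completing 2 cycles is eligible but not evaluable, so reaching 30 evaluable may take more than 30 eligible.

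If Phase 2 runs to the size in sections 3.2 and 8.2, at least four patients are treated after the point at which the toxicity rule and its printed properties end. Section 10.3 does not say whether a 6th discontinuation in the 27th to 30th patient suspends anything. This is the only numerical toxicity limit for the study as a whole; the DLT rules guide Phase 1 dosing. A DSMC or IRB member who takes 85% and 0.3% as properties of the planned Phase 2 is relying on figures for a smaller trial.

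**Working it through.** **Inputs.** From section 10.3: 4 of 12, 6 of 26, and true discontinuation rates p of 0.30 and 0.05. From sections 3.2 and 8.2: 30 patients. Patients are taken as independent with a common rate p. X_n is the number of treatment-related discontinuations among n eligible patients.

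**Step 1: the 12-patient look.** P(X_12 ≥ 4) = Σ_{k=4..12} C(12,k) p^k (1−p)^(12−k).

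- p = 0.30: 0.5075, stated as 51%.
- p = 0.05: 0.0022, stated as 0.2%.

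**Step 2: both rules, maximum N = 26.** P = P(X_12 ≥ 4) + Σ_{x=0..3} P(X_12 = x) · P(X_{N−12} ≥ 6 − x), with N − 12 = 14.

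- p = 0.30: 0.5075 + 0.0138×0.2195 + 0.0712×0.4158 + 0.1678×0.6448 + 0.2397×0.8392 = 0.8495 from unrounded terms, stated as 85%.
- p = 0.05: 0.002236 + 0.000018 + 0.000146 + 0.000412 + 0.000521 = 0.0033, stated as 0.3%.

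So all four printed figures are correct for a design with looks at 12 and 26. The overall pair does not depend on whether the second rule acts at the 6th event or only at the end. Events only accumulate, so a 6th event by patient N is the same as a count of at least 6 at N.

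**Step 3: the same rules, maximum N = 30.** Now N − 12 = 18.

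- p = 0.30: 0.5075 + 0.0064 + 0.0475 + 0.1402 + 0.2253 = 0.9269.
- p = 0.05: 0.002236 + 0.000093 + 0.000528 + 0.001074 + 0.001007 = 0.0049.

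| True rate | Stated overall | Reproduced, 26 | 6-event limit to 30 |
|---|---|---|---|
| 30% | 85% | 84.9% | 92.7% |
| 5% | 0.3% | 0.33% | 0.49% |

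**Step 4: what the last four patients add.** At a 30% rate, 1 − 0.8495 = 15.05% of trials pass patient 26 with neither rule met. Extending the limit to 30 catches a further 0.9269 − 0.8495 = 7.7 percentage points. That is about half of them (0.0775 / 0.1505 = 0.51).

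**Step 5: does the efficacy calculation settle which maximum is meant?** Take the smallest critical count with one-sided size at most 0.05 and ignore futility stops.

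- n = 30: reject at 7 or more responses; P(X ≥ 7 | 0.1) = 0.0258 and P(X ≥ 7 | 0.3) = 0.840.
- n = 26: reject at 6 or more; P(X ≥ 6 | 0.1) = 0.0399 and P(X ≥ 6 | 0.3) = 0.837.

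Both powers round to the 84% in section 8.2, so the power figure is valid for the 30 it names but does not itself rule out 26.

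**The case against.** The strongest defence is that 26 is the real ceiling. Section 3.2 says only up to 30 and adds that the actual size depends on results. Table 10.1 stops unconditionally at 26. On that reading 85% and 0.3% are right and no patient lies beyond the rule. The first part stands: 26 may be what was intended, and the figures for 26 are sound. But section 8.2 plans an enrolment of 30 without qualification, and the total of 42 needs 30 in Phase 2. One set of sections must change, and the documents do not say which.

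It can also be said that section 10.3, unlike 10.2, never confines itself to Phase 2. That is true, and the scope should be stated. Counting Phase 1 patients would widen the gap, since 42 are planned against 26.

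A reader might infer that 51% is misleading because it leaves out suspensions at patients 13 to 25. If the 6-event rule acts at once, and each discontinuation is known before the next enrolment, the chance of a halt before patient 26 at a 30% rate is 82%. The documents do not support calling 51% wrong. It is exactly the 12-patient probability, and setting early against overall reads naturally as first look against cumulative. The 85% stands in the same paragraph, and no sentence fixes when the second rule acts. The references to continuous assessment and to resuming accrual suggest immediate action, but they do not state it. That calls for a label and a sentence on timing.

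Nor do the documents leave later patients unprotected. Section 5.5 withdraws patients with drug-related grade 4 events and lets the sponsor, an investigator or the IRB stop the trial, and section 9.12.1 requires 24-hour reporting of serious events. What is missing after patient 26 is the numerical limit.

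**Conclusion.** The concern holds as a conflict over the maximum. The 6-event limit and its overall properties belong to 26 eligible patients, while the planned Phase 2 has 30 evaluable. Carrying the same limit to 30 eligible patients moves the chance of triggering a rule from 85% to about 93% at a 30% rate, and from 0.3% to about 0.5% at 5%. The change favours safety, and the false-alarm rate stays small.

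These are chances of triggering interruption or suspension and review, not of automatic termination. They assume independent patients with a common rate, a rule counted over Phase 2 patients only, and exactly 30 eligible patients. If more are enrolled to obtain 30 evaluable, both figures rise. There is no arithmetic error in section 10.3. The missing label on 51% and 0.2% and the unstated timing are minor points of wording.

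**What to change.** Choose one maximum and use it in sections 3.2, 8.2, 10.2 and 10.3.

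If it is 30:

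- In 10.3, say that the 6-event limit applies to every eligible patient enrolled, that accrual is suspended when the 6th treatment-related discontinuation occurs, and whether Phase 1 patients count.
- Restate the overall figures as about 93% at a 30% rate and 0.5% at 5%, for 30 eligible patients.
- In 10.2, replace the final row of Table 10.1 with boundaries up to 30 from the same prior and cut-off, and update the worked credible-interval example, which ends at 26.

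If it is 26: keep 85% and 0.3%, and correct sections 3.2 and 8.2 and the total of 42. With 26 evaluable patients and rejection at 6 or more responses, efficacy power would be 83.7% at a one-sided size of 4.0%. Because early toxicity stops may not be evaluable, the text must say whether 26 counts eligible or evaluable patients.

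In either case, keep 51% and 0.2% and label them as the chance of stopping at the 12-patient look.

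The cost is a few sentences, one pair of restated figures and a rerun of one small table. No extra patients, visits or data are needed beyond the 30 already planned.
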